8.1 Analysis variables

The analysis variables consist of baseline participant characteristics, safety, mAb concentration, mAb functionality, and ADA for primary- and secondary-objective analyses.

8.2 Analysis tools

Analyses for primary endpoints will be performed in SAS (v9.4). All other descriptive and inferential statistical analyses will be performed using SAS, Monolix, and/or R statistical software.

8.3 Baseline comparability

Treatment arms will be compared for baseline participant characteristics using descriptive statistics.

8.4 Safety/tolerability analysis

Since enrollment is concurrent with receiving the first study product administration, all participants will have received at least 1 product administration and therefore will provide some safety data.

8.4.1 Solicited AEs

The number and percentage of participants experiencing each type of Solicited AE sign or symptom (see Section 11.2.2) will be tabulated by severity and treatment arm and the percentages displayed graphically by arm. For a given sign or symptom, each participant's Solicited AEs will be counted once under the maximum severity for all injection visits. In addition, to the individual types of events, the maximum severity of local pain or tenderness, induration or erythema, and of systemic symptoms will be calculated. Kruskal-Wallis tests will be used to test for differences in severity between arms.

8.4.2 SAEs and Unsolicited AEs

Unsolicited AEs (see Section 11.2.2) will be summarized using MedDRA System Organ Class and preferred terms. Tables will show by treatment arm the number and percentage of participants experiencing an Unsolicited AE within a System Organ Class or within preferred term category by severity or by relationship to study product. For the calculations in these tables, a participant with multiple Unsolicited AEs within a category will be counted once under the maximum severity or the strongest recorded causal relationship to study product. Formal statistical testing comparing arms is not planned since interpretation of differences must rely heavily upon clinical judgment.

A listing of SAEs reported to the DAIDS Regulatory Support Center (RSC) Safety Office will provide details of the events including severity, relationship to study product, time between onset and last study product administration, and number of study product administrations received.

8.4.3 Local laboratory values

Box plots of local laboratory values will be generated for baseline values and for values measured during the course of the study by treatment arm and visit. Each box plot will show the first quartile, the median, and the third quartile. Outliers (values outside the box plot) will also be plotted. If appropriate, horizontal lines representing boundaries for abnormal values will be plotted.

For each local laboratory measure, summary statistics will be presented by treatment arm and timepoint, as well as changes from baseline for postenrollment values. In addition, the number (percentage) of participants with local laboratory values recorded as meeting Grade 1 AE criteria or above as specified in the Division of AIDS Table for Grading the Severity of Adult and Pediatric Adverse Events (see Section 9.8) will be tabulated by treatment arm for each poststudy product administration timepoint. Reportable clinical laboratory abnormalities without an associated clinical diagnosis will also be included in the tabulation of AEs described above.

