7.1 Inclusion criteria

General and Demographic Criteria

1. **Age** of 18 through 50 years
2. **Access to a participating CRS** and willingness to be followed for the planned duration of the study
3. Ability and willingness to provide **informed consent**
4. **Assessment of understanding**: volunteer demonstrates understanding of this study and completes a questionnaire prior to first study product administration with verbal demonstration of understanding of all questionnaire items answered incorrectly
5. **Agrees not to enroll in another study** of an investigational research agent until completion of the last required protocol clinic visit.
6. **Good general health** as shown by medical history, physical exam, and screening laboratory tests

HIV-Related Criteria:

7. Willingness to receive **HIV test results**

8. Willingness to discuss **HIV infection risks** and amenable to HIV risk reduction counseling.
9. Assessed by the clinic staff as being at “**low risk**” for **HIV infection** and committed to maintaining behavior consistent with low risk of HIV exposure through the last required protocol clinic visit (see [Appendix J](#) and [Appendix K](#)).

Laboratory Inclusion Values

Hemogram/Complete blood count (CBC)

10. Hemoglobin

- ≥ 11.0 g/dL for volunteers who were assigned female sex at birth
- ≥ 13.0 g/dL for volunteers who were assigned male sex at birth and transgender males who have been on hormone therapy for more than 6 consecutive months
- ≥ 12.0 g/dL for transgender females who have been on hormone therapy for more than 6 consecutive months
- For transgender volunteers who have been on hormone therapy for less than 6 consecutive months, determine hemoglobin eligibility based on the sex assigned at birth

11. White blood cell count = 2,500 to 12,000 cells/mm³

12. WBC differential either within institutional normal range or with site clinician approval

13. Platelets = 125,000 to 550,000 cells/mm³

Chemistry

14. Chemistry panel: alanine aminotransferase (ALT) < 1.25 times the institutional upper limit of normal (ie, < 1.25 times the reference range upper limit) and creatinine < 1.1 times the institutional upper limit of normal (ie, < 1.1 times the reference range upper limit)

Virology

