9.2 Pre-enrollment procedures

Screening may occur over the course of several contacts/visits, up to and including before study product administration on day 0. All inclusion and exclusion criteria must be assessed within 56 days before enrollment, unless otherwise specified in the eligibility criteria (or below in this section).

After the appropriate informed consent has been obtained and before enrollment, the following procedures are performed:

- Medical history, documented in the case history record;
- Assessment of whether the volunteer is at low risk for HIV infection (see [Appendix J](#) and [Appendix K](#));
- Complete physical examination, including height, weight, vital signs, and clinical assessments of head, ears, eyes, nose, and throat; neck; lymph nodes; heart; chest; abdomen; extremities; neurological function; and skin;

- Assessment of concomitant medications the volunteer is taking, including prescription and nonprescription drugs, vitamins, topical products, alternative/complementary medicines (eg, herbal and health food supplements), recreational drugs, vaccinations, and allergy shots;
- Laboratory tests including:
 - Screening HIV,
 - Hepatitis B surface antigen (HBsAg),
 - Anti-HCV Abs,
 - Syphilis,
 - Complete Blood Count (CBC) with differential,
 - Chemistry panel (alanine aminotransferase [ALT], creatinine),
 - Urine dipstick (urinalyses if indicated; see Section 9.7), and
 - Urine or serum pregnancy test (volunteers who were assigned female sex at birth); persons who are not of reproductive potential due to having undergone total hysterectomy with bilateral oophorectomy (verified by medical records) are not required to undergo pregnancy testing;
- Administration of behavioral risk assessment questionnaire;
- Obtaining volunteer demographics in compliance with the NIH Policy on Reporting Race and Ethnicity Data: Subjects in Clinical Research, Aug. 8, 2001 (available at <http://grants.nih.gov/grants/guide/notice-files/NOT-OD-01-053.html>);
- Counseling on HIV testing and risk reduction, performed in compliance with the US Centers for Disease Control and Prevention (CDC)'s current guidelines or other local guidelines for HIV counseling, testing, and referral as described in Section 9.5; and

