9.3 Enrollment and study product administration visits

Once a volunteer has consented to trial participation and is found to meet all eligibility criteria (see Sections 7.1 and 7.2), the CRS requests the randomization assignment via a Web-based randomization system. Enrollment is simultaneous with first study product administration. In general, the time interval between randomization and enrollment should not exceed 4 working days. However, circumstances may require a participant's enrollment visit to be changed. This may exceed the 4-day randomization time limit.

At all study product administration visits, the following procedures are performed **before study product administration**:

- Abbreviated physical examination, including weight, vital signs, and a symptom-directed evaluation by history and/or appropriate physical exam based on participant self-reported symptoms or complaints;
- Assessment of baseline Solicited AEs;
- Assessment of concomitant medications (as described in Section 9.2);
- Assessment of any new or unresolved Unsolicited AEs/intercurrent illnesses; and
- Clinical laboratory tests including:
 - CBC with differential;
 - Chemistry panel (alanine aminotransferase [ALT], aspartate aminotransferase [AST], alkaline phosphatase [Alk Phos] and creatinine); and
 - Urine or serum pregnancy test (for participants who were assigned female sex at birth). Persons who are NOT of reproductive potential due to having undergone hysterectomy or bilateral oophorectomy (verified by medical records), are not required to undergo pregnancy testing. For pregnant participants, see Section 9.11.

Following completion of all procedures in the preceding list, and if available results indicate that study product administration may proceed, study product administration is administered (see Sections 8.3 and 8.4).

Administration of all infusions during a study product administration visit must be accomplished within 1 calendar day.

Immediately following study product administration, the participant remains in the clinic for observation for about 1 hour. See the HVTN 140/HPTN 101 SSP for details regarding study product administration visit procedures. Before leaving the clinic, the participant is given the Participant Diary and is instructed on how to complete it. The CRS will make arrangements to be in contact with the participant as described in Section [9.8](#).

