9.3 List of Graphs

- Maximum Local Solicited AEs
- Maximum Systemic Solicited AEs
- Boxplots for Alkaline Phosphatase, AST, ALT, Creatinine, WBC, Hemoglobin, Platelets, Lymphocyte Count, Neutrophil Count

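### The graded laboratory table ignores the Day 0 grade, so it cannot separate abnormalities present before product from new ones

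*SAP*

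**What the plan says.** **The graded count.** SAP 8.4.3 and Protocol 6.4.3.3 share one rule: "the number (percentage) of participants with local laboratory values recorded as meeting Grade 1 AE criteria or above" "will be tabulated by treatment arm for each poststudy product administration timepoint". Neither text conditions on the grade before product, provides a graded Day 0 column, or plans a shift table. The output lists in SAP 9.1 to 9.3 add no graded laboratory table. Laboratory results appear there by name only as "Boxplots for Alkaline Phosphatase, AST, ALT, Creatinine, WBC, Hemoglobin, Platelets, Lymphocyte Count, Neutrophil Count".

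**Baseline use in the same section.** "Box plots of local laboratory values will be generated for baseline values" as well as for later values, by arm and visit. In addition, "summary statistics will be presented by treatment arm and timepoint, as well as changes from baseline for postenrollment values".

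**What entry allows.** Protocol 7.1 sets numeric limits for hemoglobin, WBC, platelets, ALT and creatinine. For the differential the criterion is "WBC differential either within institutional normal range or with site clinician approval". The screening panel in Protocol 9.2 is "Chemistry panel (alanine aminotransferase [ALT], creatinine". AST and alkaline phosphatase first appear in the panel drawn before product at administration visits (Protocol 9.3): "Chemistry panel (alanine aminotransferase [ALT], aspartate aminotransferase [AST], alkaline phosphatase [Alk Phos] and creatinine".

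**Comparators.** Every group in the schema receives active product, open-label.

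**The concern.** Laboratory measures of safety are part of primary endpoint 1. Under the stated rule, a participant who is already Grade 1 on alkaline phosphatase, say, before any infusion and stays there is counted after product exactly like a participant who was normal on Day 0 and then became abnormal.

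A placebo arm would show the background rate, but this trial has none. The arms hold 3 or 16 participants, so a single such case moves an arm's percentage visibly. The result is a graded table that mixes prevalence at entry with new onset and gives the reader no means of splitting the two.

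**Working it through.** **Inputs from the documents.** Arm sizes are 3 (Part A) and 16 (Part B), with 80 participants in Part B in total (schema; Protocol 6.1.1). The prevalence of Grade 1+ values before product is not given, and the DAIDS grade cut-offs are not reproduced. The prevalence q, per measure, is therefore an assumption, shown over 1% to 10%.

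**Check against the plan's own figures.** Protocol Table 6-1 gives the probability of one or more events, which is 1 − (1 − p)^n.
- n = 16, p = 10%: 1 − 0.90^16 = 0.815 (table: 0.81).
- n = 16, p = 4%: 1 − 0.96^16 = 0.480 (table: 0.48).
- n = 3, p = 10%: 1 − 0.90^3 = 0.271 (table: 0.27).

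The table reproduces, and the same formula applies below.

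**Pre-existing cases in the planned count, with no product effect.** Let q be the share of entrants with a stable Grade 1+ value on one measure before product.

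| Assumed q | At least one in an arm of 3 | At least one in an arm of 16 | Expected in an arm of 16 (16q) | Expected in Part B (80q) |
|---|---|---|---|---|
| 1% | 3% | 15% | 0.16 | 0.8 |
| 2% | 6% | 28% | 0.32 | 1.6 |
| 5% | 14% | 56% | 0.8 | 4 |
| 10% | 27% | 81% | 1.6 | 8 |

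One case adds 1/16 = 6.3 percentage points to a Part B arm and 1/3 = 33 points to a Part A arm. Counting only grades above the Day 0 grade, these stable cases contribute zero.

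**With some true new onset.** Take q = 5% and a 5% new-onset rate among the rest. The planned Part B count is 80 × (0.05 + 0.95 × 0.05) = 7.8. The above-baseline count is 80 × 0.95 × 0.05 = 3.8. About half of the planned count would be pre-existing.

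**How often one case could appear.** Safety laboratory tests are not drawn at every visit. In Appendix F (Part A) the post-product draws are Days 56 and 168. The Appendix G rows are broken in the text, but the 10 mL of safety blood can be recovered as visit total minus stored serum, and minus 10 mL of HIV diagnostics where drawn:
- Day 56: 52.5 − 42.5 = 10
- Day 112: 71 − 51 − 10 = 10
- Day 168: 52.5 − 42.5 = 10
- Day 224: 42.5 − 42.5 = 0
- Day 280: 62.5 − 42.5 − 10 = 10

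A persistent abnormality could therefore appear in up to two columns in Part A and four in Part B.

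**The case against.** A reader might infer that the plan reports pre-existing abnormalities as product toxicity. The documents do not support that. The graded table assigns no cause. Attribution is made in the adverse event tables, which are broken down by relationship to product (SAP 5, 8.4.2 and 9.1). Reportable laboratory abnormalities without a diagnosis also enter those tables. SAP 8.4.3 states no baseline rule for them, but detail is left to the study-specific procedures, which are not in hand, so that handling cannot be judged.

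Several further points narrow the concern:

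- **Entry safeguards.** Exclusion 15 removes clinically significant abnormal laboratory results, and the differential does have a default limit, the institutional normal range. This leaves room for mild graded values, though how much is unknown.
- **Baseline displays.** The Day 0 box plots show outliers and, if appropriate, lines at the abnormal boundaries, so in arms this small some abnormal Day 0 values will be visible. Neither they nor the change summaries link a participant's grade before product to the grade afterwards.
- **Site mix.** It is tempting to say that site differences would bias comparisons between arms. Groups 2 and 3, Groups 4 and 5, and Groups 6 to 9 are randomized, so an imbalance within those sets is chance. A systematic difference is plausible only for Groups 1 and 10, which are not randomized.
- **Decisions.** No test is specified on this table. Escalation and pauses rest on review of cumulative safety data and related graded events (Protocol 11.3 and 11.4).
- **Conservatism.** An all-grades count hides nothing. An above-baseline count can.

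These points limit the consequences. None of them makes the graded count able to separate old from new.

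**Conclusion.** The gap is real and modest. The graded laboratory table of a primary safety endpoint cannot distinguish pre-existing from new abnormalities, and no other planned output does so at participant level. No figure in the plan is wrong.

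The size rests on an assumed prevalence and on the Day 0 abnormality persisting. At 1% to 2% per measure, an arm of 16 more often than not has no such participant. At 5% to 10% it more often than not has at least one. The documents do not say which range applies. The measures most exposed are AST and alkaline phosphatase, which are unscreened, and the differential counts, where an out-of-range value can be approved. The point is a cheap improvement.

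**What to change.** In SAP 8.4.3, and in Protocol 6.4.3.3 if it is amended:

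1. Define baseline as the last value before first product.
2. Add, by arm and measure, a count at each post-product laboratory timepoint of participants whose grade exceeds their baseline grade.
3. Add a shift table of baseline grade by worst post-product grade, by arm and measure.
4. Keep the all-grades table beside them, and name all three in SAP 9.1.
5. State whether laboratory abnormalities carried into the adverse event tables follow the same baseline rule.

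The cost is SAP wording and programming. The Day 0 CBC and full chemistry panel are already drawn before product, so no visit, sample or clinical rule changes.

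There is one small downside. Day 0 specimens may be up to 14 days old (Appendices H and I, footnote 2), and a transient abnormality at that draw would mask a later event of the same grade in the above-baseline count. That is the reason for keeping the all-grades table.

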8.4.4 Reasons for study product administration discontinuation and early study termination

The number and percentage of participants who discontinue study product administration and who terminate the study early will be tabulated by reason and treatment arm.

8.5 Analyses prior to end of scheduled follow-up visits

Any analyses conducted prior to the end of the scheduled follow-up visits should not compromise the integrity of the trial in terms of participant retention or other study endpoint assessments.

8.5.1 Safety

During the course of the trial, unblinded analyses of safety data will be prepared approximately every 4 months for review by the SMB. Ad hoc safety reports may also be prepared for SMB review at the request of the HVTN 140/HPTN 101 PSRT.

9 SAFETY TABLES AND FIGURES

9.1 List of Tables

- Enrollment Report
- Demographics and Study Product Administration Frequencies
- Overall Protocol Status
- Discontinuation Status
- Study Product Administration Errors
- Maximum Local and Systemic Solicited AE Summaries
- Severe or Life-threatening Local Solicited AE's
- Moderate, Severe, and Life-threatening Erythema / Induration
- Adverse Experiences by Body System and Severity – By Decreasing Frequency
- Adverse Experiences by Preferred Term and Severity – By Decreasing Frequency – Includes Severe, Life-threatening or Fatal Events Only
- Adverse Experiences by Preferred Term and Severity – By Decreasing Frequency – Includes Events of All Severities
- Adverse Experiences by Preferred Term and Relationship to Study Product – By Decreasing Frequency – Includes Related Events Only
- Adverse Experiences by Preferred Term and Relationship to Study Product – By Decreasing Frequency – Includes Events of Any Relationship
- Severe, Life-Threatening, or Fatal Adverse Events
- Related Events

9.2 Participant Listings

The following listings of participant-level data are included in the SMB reports.

- Discontinuations
- Pregnancies
- Severe or Life-Threatening Local and Systemic Solicited AEs
- Moderate or Severe Erythema and Induration
- Expedited Adverse Experiences (EAEs)
- Severe, Life-Threatening, or Fatal Adverse Experiences
- Adverse Experiences with Relationship to Study Product (Grade 2 or higher)
- Study Product Administration Errors
- HIV Infection Results from Lab and Reported by Site
- mAb Reactions

9.3 List of Graphs

- Maximum Local Solicited AEs
- Maximum Systemic Solicited AEs
- Boxplots for Alkaline Phosphatase, AST, ALT, Creatinine, WBC, Hemoglobin, Platelets, Lymphocyte Count, Neutrophil Count

